5.0 Outcome Measures

5.1 Primary Outcome

5.1.1 The primary outcome will be feasibility. The data gathered will be used to inform the development of a larger future study. Feasibility

in this study will be defined as follows: the proportion of patients who agree to participate in the intervention. Among patients who agree to participate the proportion that are able to complete the intervention and document barriers to participation.

5.1.2 For all patients – both in the active and control groups, we will determine the proportion who are able to have the baseline and follow-up assessments of measures of interest (cardiovascular imaging, exercise measures (peak VO₂ and 6 min walk distance).

5.2 Secondary Outcomes

5.2.1 In the 21 patients, the following outcomes will be assessed at the first visit and then 3 and 6 months after initiating Anth-bC or other potentially cardiotoxic cancer therapies; to assess the ability to ascertain: peak exercise cardiac output, calculated A-V O₂ difference and VO₂, and pre- exercise measures of LV & cognitive function, HRQOL, six-minute walk distance (6minWD) and fatigue

Detailed descriptions of these outcomes are below.

Measurements and quality control

MRI Variables. We will measure LV volumes (including LV stroke volume and heart rate to determine exercise associated cardiac output), EF because a) these values deteriorate shortly after cancer treatment,¹⁹ b) influence exercise capacity,^{16,38,39} and c) are used clinically to guide medical therapy to reduce CV events.^{16,32,40,41} MRI has been selected as the primary assessment of cardiac and vascular function because of a) its reliability (>98% acquired valuable subjects within the Jackson Heart Study),⁴² b) its reproducibility (>98% for repeated measures in pilot data from cancer participants),²² c) its accuracy (ability to detect informative changes indicative of prognosis regarding both the cardiac and vascular systems), d) its translational capability (existing large NHLBI efforts to assess CV disease from which cross-sectional comparisons with the data set can be made),⁴³⁻⁴⁵ and e) the low variance and inter-observer variability for technologists to acquire reliable data relative to other imaging modalities such as transthoracic echocardiography, which is highly technologist dependent and exhibits high variance.

Improving Exercise Capacity with a Tailored Physical Activity Intervention in Lymphoma

and Breast Cancer Patients Undergoing Treatment – An addendum to NIH

R01CA167821 “Early Imaging Detection of CV Injury after Cancer”

Wake Forest Baptist Comprehensive Cancer Center

CCCWFU# 99112

Our images will be acquired and analyzed according to previously published techniques (for which [name] has extensive experience)^{32,46,47} using techniques from other NIH funded initiatives. Briefly, the individual will be

[figure not shown]

Figure 7: Upright Treadmill Exercise CMR-CPET Stress Test Protocol. (a) CMR scanner with shoulder harnesses (black arrows) to aid with correct patient/participant positioning (b) obtaining rest cine imaging; (c) placement of electrode patches and blood pressure cuff for patient monitoring; (d) treadmill exercise stressing with expired gases, and (e) repositioning the patient/participant into the scanner for post-stress cine images.

escorted into the scanner to allow researchers to collect resting CMR images (Figure 7). Upon completion, the participant then will perform a CPET, according to the Bruce or Modified Bruce protocol. When the individual indicated they were at their maximal capacity the test will be terminated and the subject will be immediately escorted quickly back into the scanner to collect immediate post exercise CMR measures. In our pilot data and in our publications, all post-exercise CMR data are initiated 20 seconds after exercise completes and acquisitions are completed within 50 seconds of leaving the treadmill. After the post exercise CMR is completed, the individual will be monitored to ensure that HR falls to <100 bpm during which recovery LV wall motion assessments will be made. All images will be acquired using the Siemens 1.5 Tesla Avanto scanner located in the Cardiovascular Imaging Center (Reynolds Tower, Wake Forest Health Sciences, Winston-Salem, North Carolina).

The CMR protocol is performed according to prior techniques⁴⁸⁻⁵⁰ & includes a series of white blood steady-state free precession cine images acquired in the short-axis plane to cover the entire left ventricle (LV) using a 5 to 10 second real-time, cardiac-gated, free breathing acquisitions with the following parameters: 6-10 slices of 8 mm thickness and 2 mm gap spanning the entire LV, a 128x72 matrix, a 340 x 255 mm field of view, 72 views per segment with view sharing, and echo spacing of 2.1 ms, resulting in a temporal resolution of 46 ms and voxel size of 2.6 x 2.6 x 8 mm. From these images, LV end-diastolic (LVEDV) and end-systolic (LVESV) volumes will be determined for calculation of the LV ejection fraction and stroke volume. Identical sets of volumetric images were acquired pre-exercise and post-exercise (<30 sec from maximal exercise stress test).

All images will be processed offline by an image analyst blinded to study group using Medis software (Leiden, Netherlands). For each slice of the cine stack obtained, pre- and post-exercise, the endocardial border of the myocardium will be contoured to determine the area of the LV blood pool at both end-systole

Improving Exercise Capacity with a Tailored Physical Activity Intervention in Lymphoma and Breast Cancer Patients Undergoing Treatment – An addendum to NIH
R01CA167821 “Early Imaging Detection of CV Injury after Cancer”
Wake Forest Baptist Comprehensive Cancer Center
CCWFU# 99112

and end-diastole. Using Simpson's rule, the areas will then be summed together and multiplied by the slice volume plus slice gap to determine LVEDV and LVESV.⁵¹ Ventricular volumes and cardiac output will be indexed to the subject's body surface area and expressed as mL/m² or L/min/m². Brachial artery blood pressure (BP) and heart rate (HR) will be recorded during volumetric image acquisition. Cardiac output will be calculated from the LV stroke volume multiplied by the HR during CMR acquisition. For quality control, A complete double reading on 15% of the CMR cases will be performed for quality control purposes. The reader variability results will be reported at 3-month intervals or if a change in personnel could affect image analysis and interpretation. Any scans with irregularities will be subjected to expert review. Like other studies conducted over the past 7 years, these images will also be used for data interpretation and for education purposes.

Maximal (peak VO₂) and (6-minute walk) exercise capacity outcomes. In this study, measures of both maximal (peak VO₂)^{22,33,34,52-56} and sub-maximal (6-minute walk) exercise capacity will be obtained. Peak VO₂ is selected as the primary outcome measure because it is the most reproducible measures of exercise capacity and integrates the physiologic response to exercise.^{22,33,34,52-56} It provides an objective threshold of disability and a metric that forecasts adverse cardiac prognosis as well as a parameter that can be utilized to modify medical regimens to reduce the likelihood of morbidity and mortality.^{22,33,34,52-56} It is feasible in large multi-center studies, it is reproducible and standardized. It is semi-automated and is relatively inexpensive to perform. Our team of investigators has extensive experience with using peak VO₂ as a primary measure.^{22,33,34,53,54} Amongst 3 studies for which our team serves as the core lab, the reproducibility and variance of the measure in elderly individuals (>65 years old) or those with evidence of congestive HF ranges from 7% to 12% in repeated measures.^{22,33,34,52-56} We will also perform a 6-minute walk, widely used in trials of physical function interventions, measurement that is relatively easy to administer and quite feasible and provides a very accurate assessment of sub-maximal exercise capacity. Similar to peak VO₂, the 6-minute walk is an independent predictor of CV mortality. Its acquisition will allow cross comparisons of data from this cohort with other large NHLBI sponsored multi-center initiatives. Our investigative team has utilized the 6-minute walk as an outcome measure in studies of exercise interventions in individuals treated for cancer.^{57,58}

The 6-minute walk will be administered by trained study personnel using a long, enclosed corridor with a cone placed at each end of the course. Participants will be allowed to use any mobility aids they traditionally use. Participants will be instructed to walk from end to end at their own pace while attempting to cover as much ground as possible in the six minutes.

Improving Exercise Capacity with a Tailored Physical Activity Intervention in Lymphoma and Breast Cancer Patients Undergoing Treatment – An addendum to NIH
R01CA167821 “Early Imaging Detection of CV Injury after Cancer”
Wake Forest Baptist Comprehensive Cancer Center
CCWFU# 99112

Cardiopulmonary Exercise Test as part of the MRI acquisition

After obtaining resting CMR images, the participant will perform a CPET on the treadmill following the Bruce or Modified Bruce protocol, based on current fitness level (Figure 7). Speed and grade of the treadmill will be increased gradually every three minutes until the participant reaches volitional fatigue. Throughout the CPET, ECG, rate of perceived exertion (RPE) and BP will be monitored regularly, and expired air will be collected continuously through a one-way breathing mask to determine VO₂ peak and other cardiopulmonary measures.

The metabolic system used to collect the expired gases will be calibrated, according to the manufacturer's specifications, before each test. During the CPET, a 12-lead ECG will be continuously monitored and printed at the end of each 3-minute stage. Any arrhythmias or ST-segment changes that occurred will be documented. Blood pressure and RPE will be taken during the last minute of each stage and recorded. Oxygen uptake and respiratory equivalence ratio (RER) will be monitored continuously throughout exercise. The goal for each subject will be to exceed an RER of 1.05 indicating maximal effort. Throughout the CPET, the staff will maintain constant communication with the participant to determine when the participant is at their final 30 seconds of exercise. At this point, the staff will complete a peak exercise 12-lead ECG, disconnect the electrodes, and transfer the participant to the CMR scanner. The test will be discontinued if the participant has complaints of angina or ST-segment depression >1.5 mV, or if the staff decides to terminate the test in accordance with established test termination criteria.⁵³⁻⁵⁵

Following the CPET a report is generated including a time-down report (30 second averaged) of VO₂ (ml/kg/min), VO₂ (L/min), VCO₂, METS, RER, VE, RR, FEO₂, FECO₂ and a plot for ventilatory threshold (VAT) determination. Heart rate will be determined from the ECG tracings.

Fatigue and health-related quality of life questionnaires. The Functional Assessment of Cancer Therapy–Fatigue scale (FACT-fatigue) will be used to assess fatigue.⁵⁹ The FACT-fatigue scale is 13-item scale that has been widely used in many studies to assess cancer related fatigue. The 42-item Functional Assessment of Cancer Treatment–Lymphoma (FACT-Lym) and the 37-item FACT-B questionnaires will be used to assess disease-specific HRQOL. The FACT-Lym and FACT-B measures are composed of the FACT-General which assesses four primary HRQOL domains: physical well-being (PWB), social well-being (SWB), and emotional well-being (EWB); and an additional sub-scale that measures patient concerns related to lymphoma or breast cancer (e.g., pain, fever, swelling, fatigue, and loss of appetite). The MOS 36-item Short Form Health Survey (SF-36) will also be used as a general measure of health status. The SF-36 is perhaps the most widely used measure of health status and includes domains of vitality and physical function. A 6-item measure

of self-efficacy for exercise will be used to assess confidence in walking at a moderately fast pace for increments of 10 to 60 minutes.

Cognitive function. Based on studies of chemotherapy and cognition, cardio-function and cognition and statin therapy and cognition, we propose a battery of validated neurocognitive measures (Hopkins Verbal Learning Test-Revised, Digit Span-Backward, Controlled Oral Word Association and Trail Making Test). These tests will evaluate verbal memory, attention/concentration, working memory, language, psychomotor speed, processing speed, and executive functions, according to standardized procedures utilized currently in multiple studies by [name], including one with [name] (RO1HL118740). Additionally, key patient reported outcomes (cognitive symptoms, fatigue, mood, pain, social and physical functioning and sleep) will be assessed. Following standardized procedures used in other studies by this research team, staff will be trained in the administration of all questionnaires. Each questionnaire will be self-administered and then reviewed by a study interviewer for completeness before being uploaded into the Oncore database. A study team member will be trained to administer and scoring of all cognitive tests following standardized procedures used in other studies of cognition and cancer conducted by members of this research team.

Participants will be given the option to complete these questionnaires electronically at their convenience prior to their research visits using a link to the secure web application REDCap.

Alternatively, if in person testing is either restricted or participants prefer, we would like to be able to carry out a limited battery of physical tests that can be safely completed in the home. In addition to the self-reported data that will be collected via REDCap (as per protocol) we are planning to send a sanitized container with the following contents (see Appendix P):

1. Detailed instruction packet for completing the test battery, including:
 - a. Balance test
 - b. Grip strength test
 - c. 6-minute walk test
 - d. Chair stand test
2. A smartphone that is not connected to the internet or cellular service, but which contains software for administering a balance assessment.
3. A grip strength dynamometer for measuring upper body strength
4. The previously approved Actigraph device for assessing physical activity patterns over a 7-10-day period.

Improving Exercise Capacity with a Tailored Physical Activity Intervention in Lymphoma and Breast Cancer Patients Undergoing Treatment – An addendum to NIH
R01CA167821 “Early Imaging Detection of CV Injury after Cancer”
Wake Forest Baptist Comprehensive Cancer Center
CCWFU# 99112

5. A 15-meter length of rope to mark out the course for a 6-minute walk test and 4-meter walk test.
6. A return shipping label to use to return the exercise kit to the research team after completion of home based testing

Once participants have received the box containing the equipment for completing a short battery of tests designed to measure some of the outcomes in the original procedures, we will identify a time for them to complete the tests. During the initial exercise testing and program initiation (home or supervised) we will teach participants how to use rating of perceived exertion (RPE) and how it relates to intensity (heart rate response, dyspnea). Given the focus on home-based programming, we also emphasize the importance of monitoring their daily symptoms and response to previous exercise sessions. Any concerns can be communicated to the intervention staff prior to starting exercise. Additionally, the study team has access to and will regularly monitor the heart rate and sleep data of participants in order to track their status continuously. To begin the testing session, we will contact the patients via video conferencing software and go over the instructions for completing the tests. For the balance test, the chair stand test and the walking tests, the study participant, the spouse/partner, and the study team will confirm that all tests can be completed in a safe area that is free of obstructions and that the ground is even/level. This will be done to minimize the possibility of injury. The first goal is to familiarize the participants with the smartphone, so they can operate the app for testing balance, and access and use the video camera for recording the tests. At this time, we will ask the participants spouse/partner to also familiarize themselves with the toolkit as they will be asked to take a series of short videos as the participant completes the tests. For security purposes this device is not connected to the internet so there is a reduced chance the material will be compromised. Instead, videos taken will be downloaded from the device once it is received by the PI.

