6.0 Analytic Plan

We will enroll 21 patients with 14 in the PAI and 7 in HLI. The goal of this study is to determine feasibility and preliminary efficacy data. We now describe these measurements.

Feasibility:

We will determine the proportion of patients who agree to participate in the intervention. Next, among patients who agree to participate we will determine what proportion are able to complete the intervention and document barriers to participation. For all patients – both in the active and control groups, we will determine the proportion who are able to have the baseline and follow-up assessments of measures of interest (cardiovascular imaging, exercise measures (peak VO₂ and 6 min walk distance).

In addition, for the patients receiving the active intervention we will assess the change in outcomes of interest to determine preliminary efficacy estimates. The control patients will also provide some preliminary efficacy assessments.

With 21 patients we can estimate a 95% exact confidence interval (using the Clopper-Pearson method) for the proportion of patients who have measurements taken with a width of 0.578 (i.e., from 0.211 to 0.789 if the observed proportion is 0.5 – most conservative assumption).

For estimating the outcomes of interest, a 95% confidence interval will extend +/- 0.769 standard deviation if there are 8 patients in the active group, +/- 0.635 if the sample size is 12 and +/- 0.554 SDs if the sample size is 15.

A number of assessments will be made on the patients enrolled. These include measures of peak exercise cardiac output, calculated A-V O₂ difference and VO₂, and pre- exercise measures of LV & cognitive function, HRQOL, six-minute walk distance (6minWD) and fatigue. For each of these measures we will calculate descriptive statistics in order to get some preliminary data concerning the mean values and variability of these measures. We will also obtain mean and variability values of the MRI cardiac function and HRQOL data from the 47 lymphoma patients in the parent study that did not undergo the two arms of the intervention as noted in this pilot addendum. This information will be helpful for designing a future clinical trial.

Improving Exercise Capacity with a Tailored Physical Activity Intervention in Lymphoma and Breast Cancer Patients Undergoing Treatment – An addendum to NIH
R01CA167821 “Early Imaging Detection of CV Injury after Cancer”
Wake Forest Baptist Comprehensive Cancer Center
CCWFU# 99112

Accrual:

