Date of scan: _____ Tech: _____ Time: _____ Visit #: _____ Height: _____ inches Weight: _____ lb	Participant Name/MRN and Study ID / Label Here		
BASELINE	Series#	Record INVIVO BP/HR(MRITech)	INVIVO STRIP HR (Nurse)
Localizers		BP: _____ / _____ HR: _____	HR: _____

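### The cardiac MRI analyst is to be blinded to arm, but nothing masks visit or reading order, while preliminary LV efficacy is a change over time within the active arm

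*Combined protocol and SAP*

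**What the plan says.** **Reading.** Section 5.2 (MRI Variables) says that "All images will be processed offline by an image analyst blinded to study group using Medis software". For each slice, before and after exercise, "the endocardial border of the myocardium will be contoured to determine the area of the LV blood pool" at end-systole and end-diastole. LV volumes, ejection fraction, stroke volume and cardiac output all follow from those areas. Quality control consists of a second reading of 15% of cases, reader-variability reports every 3 months or when a staff change could matter, and expert review of irregular scans.

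**Timing.** Section 5.2.1 says that "the following outcomes will be assessed at the first visit and then 3 and 6 months after initiating Anth-bC" or other potentially cardiotoxic therapy. Among its reasons for measuring LV volumes and EF, the section says that they worsen soon after cancer treatment.

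**Analysis.** Section 6.0 states "We will enroll 21 patients with 14 in the PAI and 7 in HLI". It then says that "for the patients receiving the active intervention we will assess the change in outcomes of interest to determine preliminary efficacy estimates", and adds: "The control patients will also provide some preliminary efficacy assessments". The same section names cardiovascular imaging among the measures of interest. It specifies no contrast between the arms.

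**Paperwork.** In Appendix C, images are registered under a study ID and an acrostic, and an MRI completion form goes through the coordinator to the reading centre. The CPET Stress MRI Encounter Form in the same appendix begins "Date of scan: _____ Tech: _____ Time: _____ Visit" and also has a field for the visit number.

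**The concern.** Blinding a reader to arm protects a comparison between arms. It does not protect a comparison between visits within one arm, because every participant in that arm contributes a baseline and a follow-up reading. What matters there is whether the reader knows, or can work out, which scan came first, and whether reading habits move between the two readings.

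Two mechanisms are plausible from the protocol's own text. The first is expectation: the protocol itself anticipates that LV values fall after treatment. The second is drift: if scans are read as they arrive, each baseline is read about 3 and 6 months before its follow-ups, so any movement in contouring practice, or a change of reader, lines up with visit. Variability reporting every 3 months suggests such rolling reading but does not state it.

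If either mechanism operates, its effect cannot be separated from a real change in LV function in the active-arm estimate. Section 6.0 intends these means and variances to help design a later trial, so a shifted LV change would carry into that design.

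**Working it through.** **1. Set the passages side by side.**

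| Question | What the protocol provides |
|---|---|
| Is the analyst blinded to arm? | Yes (Section 5.2) |
| Is the analyst blinded to visit or scan date? | Not stated anywhere |
| Is the reading order randomised? | Not stated anywhere |
| What is the efficacy quantity? | Change over time in the active arm (Section 6.0) |
| Is a between-arm contrast specified that would cancel a shift common to both arms? | No; controls give some preliminary assessments only |

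Write the observed change for participant *i* as D_i + b, where D_i is the change under consistent reading and b is a systematic reading shift between baseline and follow-up. The active-arm mean then estimates mean(D) + b. Arm blinding tends to make b equal in the two arms. That helps only if the arms are subtracted, and no subtraction is specified.

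**2. The plan's own precision figures.** Section 6.0 gives 95% half-widths in SD units. The formula is t(0.975, n−1)/√n.
- n=12: 2.201/3.464 = 0.635, as stated.
- n=15: 2.145/3.873 = 0.554, as stated.
- n=8: 2.365/2.828 = 0.836, where the plan states 0.769. That figure is the value for n=9 (2.306/3). The mismatch does not affect this point.
- n=14, the planned active arm: 2.160/3.742 = 0.577.

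**3. Illustration of what a shift would do.** The documents give neither an SD of change nor a size of reader shift, so b is assumed, in units of the SD of change. The interval mean ± t·s/√n covers the true mean change when a noncentral t variable with n−1 degrees of freedom and noncentrality b√n lies within ±t(0.975, n−1).

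| Assumed b (SD of change) | b√n at n=14 | Coverage, n=14 | Coverage, n=12 |
|---|---|---|---|
| 0 | 0 | 0.950 | 0.950 |
| 0.10 | 0.374 | 0.936 | 0.938 |
| 0.25 | 0.935 | 0.860 | 0.876 |
| 0.50 | 1.871 | 0.590 | 0.647 |

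For any given shift, coverage is lower at n=14 than at n=12. The bias stays fixed while the interval narrows, so recruiting more patients does not cure it.

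**4. What the existing quality control catches.** If every scan is obtained there are 21 × 3 = 63 studies, and 15% of 63 is about 9. Second reads and 3-monthly reports bear on drift and on disagreement between readers. They would not reveal an expectation held by two readers who both know the order, because such readers can agree with each other and still be shifted together.

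**The case against.** The strongest reply is that the protocol is silent rather than wrong, and that the stakes are low. Most of that stands.

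- **Knowledge of visit.** A reader might infer that the analyst will see the scan date and visit number. The documents do not say so. The form sent to the reading centre is called the completion form, the visit field is on the encounter form, and nothing says that these are the same document or that either reaches the analyst. Whether dates remain in the analysis headers is not stated, nor is it stated that contours are drawn by hand without automation. Section 5.2 also defers to published techniques that are not reproduced. What remains is that only arm blinding is promised.
- **Drift.** A reader might think of drift over the whole two-year study. Change scores are exposed only to drift within a participant's span of about 6 months, and the existing reports bear on it.
- **Concurrent controls.** The 7 controls are scanned on the same schedule, so a shift common to both arms would cancel in a between-arm difference. That is correct, but none is specified.
- **Limits of the estimate itself.** A within-arm change during cardiotoxic therapy mixes the therapy's effect with the intervention's, and visit masking does not separate them. A reader who expects decline would also bias against the intervention, not for it. Both points are fair. Neither makes a shifted estimate useful for planning.
- **Parent-study comparison.** It is tempting to say that LV change will be set against untreated patients. The protocol says that MRI data will be compared and that means and variability will be obtained; it does not say change. Those patients lacked the two study interventions, and nothing says they lacked cancer therapy.
- **Size.** One might express a shift of a few EF points as a share of the fall of more than 10% in LVEF cited in the Introduction. That would need an assumed shift and an assumed baseline EF, and it would divide a mean bias by a threshold for individual patients. It does not measure bias in the planned mean change.

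**Conclusion.** The point holds as a gap in the reading plan. The protocol blinds the analyst to study group, leaves visit, date and order unaddressed, and relies on a within-arm change that arm blinding cannot protect. It does not show that the analyst will be unmasked to visit, or that a bias will occur in a known direction.

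The size of any bias cannot be derived from the documents. Under assumed shifts of 0.1 to 0.5 SD of change, true coverage at n=14 falls from 0.95 to between about 0.94 and 0.59, so the consequence ranges from negligible to serious depending on a quantity the plan does not give. The reach is limited: LV function is a secondary, descriptive outcome in a feasibility pilot, no test or decision threshold rests on it, and the primary feasibility proportions are unaffected. The change is worth making because it is cheap, and because it must be made before endpoint reading to avoid re-reading scans.

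**What to change.** Replace the blinding sentence in Section 5.2 with wording such as:

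> Images will be processed by an analyst blinded to study group and to visit; scan date and visit number are removed or replaced by a random code before endpoint reading, and each participant's available baseline, 3- and 6-month studies are contoured together in random order after that participant's last scan; the same masking applies to second reads.

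Keep any safety review of images separate from this endpoint reading, so that masking delays nothing needed for participants. State also that forms carrying the date or visit number are not passed to the analyst.

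The cost is recoding image headers and keeping a random reading list for at most 63 studies. No extra reader, scan or patient visit is needed. The small downside is that endpoint readings wait for each participant's last scan, so reader-variability reports start later than they would under rolling reading.
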